Study Protocol and Statistical Analysis Plan

Behavioral Interventions to Reduce Heavy Drinking Among MSM in HIV Primary Care

NCT02709759

April 2, 2024

Description and Purpose of the Project

The purpose of this project is to conduct a randomized clinical trial in which 224 heavy drinking men who have sex with men (MSM), who receive their HIV primary care at Fenway Health or other health care facilities in the greater Boston area or Jackson Memorial Hospital Medical Center or other health care facilities in Miami (N = 112 per site), are randomly assigned in a 2 X 2 X 2 design to receive either (1) Brief Advice about their drinking (BA) or Motivational Interviewing (MI) with personalized normative feedback specific to their drinking and HIV. Participants will also be assigned to receive either (2) an interactive text messaging (ITM) system that facilitates behavioral self-monitoring versus no ITM and (3) a standard (1-month) vs. an extended intervention (9 months; EI). BA and MI will be delivered by interventionists at Brown University using a webcam-enabled telemedicine system, as well as over the phone. Both BA and MI will involve one individual session of up to an hour, conducted using videoconferencing, and a follow-up counseling session delivered over the phone a month later that can last up to 20 minutes (5-10 minutes for BA, 10-20 minutes for MI). BA will involve counseling patients that they are drinking more than recommended limits for safe consumption and that staying below these limits is important for those with HIV. The MI intervention involves a more in-depth discussion of alcohol use, including providing feedback on health indicators and alcohol and other substance use. The ITM program involves sending/receiving text messages about participants' drinking daily for 30 days. The EI conditions involve extended versions of either counseling approach (BA vs. MI) and the ITM program. Beyond the "standard" counseling participants receive, those in the EI conditions will receive additional 5-20 minute phone-based counseling sessions at 3- and 9- months, and participate in an additional 5-20 minute videoconference session at 6 months. Those in the EI+ITM condition will participate in an extended version of the ITM program that provides interactive text messages each week for 8 additional months after the initial 30 days (months 2-9).

The primary aims of the study are as follows:

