Missing data. We conducted our primary analyses using complete data. We also used re-ran analyses with imputed data as a sensitivity analysis. Imputation of missing data was carried out using the chained-equation method (R MICE package) assuming that data were missing at random. We maintained the longitudinal structure of the data and built imputation models that imputed missing values at 6 months only using baseline data and observed 6-month data, and imputed the missing values at the 12 months using baseline and imputed 6-month data and observed 12-month data. Imputations were iterated until the distribution of imputed values stabilized. Five complete datasets were created and used for regression analyses. The results were then pooled using Rubin's method^{56,57}.

References

- 2. Radloff LS. The CES-D scale: A self-report depression scale for research in the general population. *Applied Psychological Measurement*. 1977;1(Summer):385-401.

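### The only missing-data sensitivity analysis pools five imputed datasets, so its p-values carry appreciable Monte Carlo error; the primary analysis is not affected

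*Combined protocol and SAP*

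**What the plan says.** The missing-data paragraph of the Statistical Analysis Plan sets out two analyses. The main one does not impute: "We conducted our primary analyses using complete data". The second is a check on it: "We also used re-ran analyses with imputed data as a sensitivity analysis". That check uses chained equations in R, "assuming that data were missing at random", and Rubin's rules for pooling. The number of datasets is fixed: "Five complete datasets were created and used for regression analyses".

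The paragraph also says "Imputations were iterated until the distribution of imputed values stabilized". This concerns the convergence of each chain. It does not concern how many completed datasets are pooled, so it has no bearing on the Monte Carlo error of the pooled result.

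Nothing elsewhere changes the number five, justifies it, fixes a seed or asks for a Monte Carlo error. No other missing-data sensitivity analysis is described. The documents give no expected missing rate, no significance level, and no rule for deciding whether the imputed and complete-data results agree.

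**The concern.** A sensitivity analysis is useful if a difference from the primary result can be read as an effect of the missing data. With few imputations, part of any difference is random noise from the imputation draws. If readers compare the two analyses by whether each p-value falls below 0.05, which is a common habit and is not ruled out here, another seed could turn apparent support into apparent conflict, or the reverse, with the same data, model and assumptions.

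There is room for this to happen. Equation 1 contains seven factorial terms (three main effects, three two-way and one three-way interaction). If a separate model is fitted for each outcome and time point, there are 2 × 2 = 4 primary models and 2 + 2 + 1 = 5 secondary models, so 9 × 7 = 63 coefficients. Some are likely to fall near 0.05.

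**Working it through.** The plan has no figure of its own to reproduce here, so the check asks how far the pooled result moves when only the seed changes.

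**Inputs.** From the plan: m = 5, Rubin pooling. Assumed, because the documents are silent: fraction of missing information (FMI) of 10%, 20% and 30%, with 5% as a low case; two-sided 0.05; complete-data degrees of freedom of 210, for 224 planned participants less the model terms.

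**Set-up.** Scale the total variance with infinitely many imputations to 1. Between-imputation variance is then B = FMI and within-imputation variance is W = 1 − FMI. The converged p is the one obtained with infinitely many imputations.

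**Step 1: noise in the pooled estimate.** Its Monte Carlo SD, in standard-error units, is √(FMI/m). At 20%: √(0.20/5) = 0.200 and √(0.20/50) = 0.063. Relative efficiency is 1/(1 + FMI/m): 1/(1 + 0.20/5) = 0.962 for five. Little precision is lost.

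**Step 2: noise in the test statistic.** The test divides the estimate by √T, with T = W + (1 + 1/m)B, and B is itself estimated on m − 1 degrees of freedom. For five datasets at 20% and a converged statistic of 1.96:

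- mean T = 0.80 + 1.2 × 0.20 = 1.04
- SD of T = 1.2 × 0.20 × √(2/4) = 0.170
- contribution of the estimate: 0.200/√1.04 = 0.196
- contribution of T: (1.96/√1.04) × 0.170/(2 × 1.04) = 0.157
- SD of the statistic ≈ √(0.196² + 0.157²) = 0.25

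For fifty, T = 1.004, SD of T = 1.02 × 0.20 × √(2/49) = 0.041, and the same sum is √(0.063² + 0.040²) = 0.075. Simulation of full Rubin pooling agrees:

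| FMI | SD of estimate (SE units), m = 5 / 50 | SD of test statistic, m = 5 / 50 | Relative efficiency, m = 5 |
|---|---|---|---|
| 10% | 0.141 / 0.045 | 0.16 / 0.05 | 0.980 |
| 20% | 0.200 / 0.063 | 0.25 / 0.075 | 0.962 |
| 30% | 0.245 / 0.077 | 0.32 / 0.10 | 0.943 |

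**Step 3: what this does to p.** Each simulated seed draws the estimate and B, forms T, and reads p from a t distribution with Barnard-Rubin degrees of freedom. At 20% missing information:

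| Converged p | m | 95% seed range of p | Seeds with p ≥ 0.05 |
|---|---|---|---|
| 0.04 | 5 | about 0.013-0.137 | 46% |
| 0.04 | 50 | about 0.029-0.059 | 16% |
| 0.02 | 5 | not needed | about 15% |
| 0.02 | 50 | not needed | essentially none |

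**Step 4: sensitivity to convention.** The rows above place the converged p on the normal scale. The limiting degrees of freedom are (211/213) × 210 × 0.80 = 166, so a normal p of 0.04 is about 0.042 on the t scale. Defining the converged p as 0.04 on the t scale gives 0.013-0.132 and 43% for five datasets, and 0.028-0.057 and 12% for fifty. The message does not change.

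**Step 5: low missingness (t-scale convention).** At 5% FMI and five datasets, about 0.1% of seeds cross 0.05 when the converged p is 0.02 or 0.10. Close to the threshold it still matters: 22% of seeds cross at 0.04 and 20% at 0.06.

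**The case against.** Several objections stand and limit the point.

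- **The primary conclusion does not depend on a seed.** A reader might infer that the trial's main result could change with the random draws. It cannot: the primary analysis uses complete data and imputes nothing.
- **Five imputations are not inefficient.** A reader might infer that the imputed analysis is invalid or badly imprecise. Relative efficiency is 94-98% over the assumed range, and Rubin's rules allow for a small m. The weakness is reproducibility of the p-value.
- **The plan sets no agreement rule.** It states neither an alpha nor that the imputed analysis must cross 0.05. Comparing estimates and intervals is an equally open reading, and on that reading the harm is smaller. The estimate still moves by 14-24% of its standard error between seeds.
- **More imputations do not cure the threshold problem.** Exactly at 0.05, two seeds disagree about half the time for any finite m. Five datasets widen the affected band; they do not create it.
- **The size rests on assumed missing information.** The follow-up section offers telephone visits to participants who move away, so FMI below 10% is possible, though the documents do not show it.

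What does not stand is the view that high relative efficiency settles the matter. Efficiency describes the precision of the estimate, and it does not measure how far a p-value moves when the imputations are redrawn. The statement on iterating to stability does not settle it either.

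**Conclusion.** The point holds as a minor one about reproducibility. The plan's single missing-data sensitivity analysis uses too few imputations for its p-values to be stable near a decision threshold. Under 10-30% missing information, moving from five to fifty datasets cuts the seed-to-seed SD of the test statistic to about a third (0.16-0.32 down to 0.05-0.10). At 20% and a converged p of 0.04, the share of seeds landing on the other side of 0.05 falls from 46% to 16%.

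These sizes depend on the FMI range, the two-sided 0.05 threshold and the assumed degrees of freedom, none of which the documents give. With little missing information the effect is confined to results very close to 0.05. The documents do not support a claim that the primary findings are unreliable, or that any particular sensitivity result is wrong.

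**What to change.** Replace five with at least 50 imputed datasets, and use 100 if the estimated fraction of missing information exceeds 30%. These numbers are working choices and not derived optima. At 30% missing information they bring the Monte Carlo SD of the estimate from 24.5% of its standard error (m = 5) to 7.7% (m = 50) or 5.5% (m = 100). Record the seed. Report the estimated fraction of missing information and the Monte Carlo error of the pooled estimates. State that the imputed and complete-data analyses will be compared on estimates and confidence intervals as well as p-values. The SAP is written in the past tense, but the imputation can be re-run without new data or a change of model or assumption.

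The cost is computing time and some checking. Each extra dataset needs another set of marginalized zero-inflated negative binomial fits with the factorial terms and interventionist indicators, and convergence should be confirmed in every dataset before pooling.
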